3. OVERALL STUDY DESIGN AND PLAN DESCRIPTION

3.1. STUDY DESIGN

The study will be a phase 2, multicentre, double-blind study. It has been designed to investigate (proof of concept) whether ladarixin has sufficient activity (preservation of β -cell function and slow-down of the progression of T1D) to warrant its further development.

It will involve 72 patients with new-onset T1D. Patients will be randomly (2:1) assigned to receive either ladarixin treatment (400 mg b.i.d. for 3 cycles of 14 days on/14 days off - treatment group) or matched placebo (control group). The two groups will be balanced within centres.

Recruitment will be competitive among the study sites, until the planned number of patients is enrolled. Competitive recruitment has been chosen to increase the speed of recruitment and to account for any difference among study sites in the rate and timing of patient referral. Each site will recruit patients as rapidly as possible up to a maximum of 21 patients (as per randomization list).

Each patient will be involved in the study for a screening period of up to 100 days followed by a post-randomization period up to 52 \pm 2 weeks, as per details below:

- a screening period including 2 or more visits during a period up to 100 days; this includes the time required to confirm the diagnosis;
- a treatment period including 3 treatment cycles of 2 weeks each with 2 weeks interval between cycles and 2 corresponding pre-dose assessment visits;
- 3 follow-up visits scheduled at weeks 13 \pm 1 (month 3), 26 \pm 2 (month 6) and 52 \pm 2 (month 12).

Sample size calculation has been based on the 2-hour area under the curve (AUC) of C-peptide response to a Mixed Meal Tolerance Test (MMTT) observed 12 months after randomization, as these are the only available data that best match the T1D population expected to be randomized in this trial (age, time from diagnosis, etc.) [Lachin, 2011]. On the other hand, the time frame for the primary endpoint (2-hour AUC of C-peptide response to the MMTT) has been set at week 13 \pm 1 in order to maximise the potential to observe an effect of ladarixin, considering the PK profile in humans as well as the reversibility of the pharmacological effect on CXCR1/2 receptors. Such an approach is appropriate for a phase 2 proof of concept trial. Follow-up is anyway extended up to 12 months.

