8.2. RECORDING

AE data should be obtained through observation of the patient, from any information volunteered by the patient, or through patient questioning.

All AEs (serious and non-serious) which occur from enrolment through patient participation in the study (last planned visit or early withdrawal date) will be reported and recorded in the CRF. It is important that this includes the duration of the AE (onset/resolution dates), the relationship to the drug, the severity, the outcome and relevant concomitant treatments dispensed (or other action taken).

All AEs should be followed-up to determine outcome of the reaction. The Investigator should follow up the event until resolution or stabilization of the condition. It is the Investigator's responsibility to assure that the subjects experiencing an AE receive definite treatment for any AE, if required.

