8.2.2. Severity of AEs

The Investigator will grade the severity of any AE using the definitions in the **Table below**. For each episode, the highest severity grade attained should be reported.

Severity of the Adverse Event

Mild	Grade 1 - Does not interfere with patient's usual function (awareness of symptoms or signs, but easily tolerated [acceptable]).
Moderate	Grade 2 - Interferes to some extent with patient's usual function (enough discomfort to interfere with usual activity [disturbing]).
Severe	Grade 3 - Interferes significantly with patient's usual function (incapacity to work or to do usual activities [unacceptable])

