### 16.4.3. ADVERSE EVENTS

All AEs will be assigned to a Preferred Term (PT) and will be classified by primary System Organ Class (SOC) according to the MedDRA thesaurus version 19.1 or higher.

Any AE which started at or after the first administration of study treatment will be considered a Treatment Emergent Adverse Event (TEAE).

Each AE will be graded according to severity definitions as “Mild”, “Moderate” or “Severe”.

Summary of TEAEs will be presented for the SAF set by treatment group.

If the start date is missing for an AE, the AE will be considered to be treatment emergent (See Appendix 2 for more details about how to handle with partial or missing start/stop dates).

TEAEs will be reported on a per-patient basis. This means that even if a patient reported the same event repeatedly (i.e. events mapped to the preferred term) the event will be counted only once.

For summaries, the drug-event relationship will be assessed as “None”, “Unlikely”, “Possible” “Probable” or “Highly probable”. Any TEAE reported in the study having a possible, probable or highly probable relationship to study drug will be defined as “Adverse Drug Reaction” (ADR).

The following tables and listings will be presented:

- 1) An overview of TEAEs including the number of patients who exhibited at least one TEAE, at least one serious TEAE, at least one non-serious TEAE, at least one ADR, at least one serious ADR, number of TEAEs, number of non-serious

---

Document:	MEX0114_SAP_v4_4 Final Methods.docx	Version Number:	Final Version 4.4
Author:	[name]	Version Date:	[17SEP2019]

Template No: CS\_TP\_BS016 – Revision 4  
 Effective Date: 01Apr2016

Reference: CS\_WI\_BS005

TEAEs, number of TESAEs, number of ADRs, number of serious ADRs, number of deaths, number of patients who discontinued study drug due to a TEAE;

- 2) Summary of TEAEs by primary System Organ Class and Preferred Term;
- 3) Summary of TEAEs by primary System Organ Class, Preferred Term and Severity;
- 4) Summary of Serious TEAEs by Primary System Organ Class and Preferred Term;
- 5) Summary of ADRs by Primary System Organ Class and Preferred Term;
- 6) Summary of TEAEs leading to Study Drug Discontinuation by Primary System Organ Class and Preferred Term;
- 7) Summary of TEAEs leading to Death by Primary System Organ Class and Preferred Term;
- 8) Line Listing of all AEs by Patient;
- 9) Line Listing of SAEs by Patient;
- 10) Line Listing of Adverse Drug Reactions by Patient;

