## APPENDIX 2. PARTIAL DATE CONVENTIONS

Algorithm for Treatment Emergence of Adverse Events:

START DATE	STOP DATE	ACTION
Known	Known	If start date < study med start date, then not TEAE If start date >= study med start date, then TEAE
	Partial	If start date < study med start date, then not TEAE If start date >= study med start date, then TEAE
	Missing	If start date < study med start date, then not TEAE If start date >= study med start date, then TEAE
Partial, but known components show that it cannot be on or after study med start date	Known	Not TEAE
	Partial	Not TEAE
	Missing	Not TEAE
Partial, could be on or after study med start date	Known	If stop date < study med start date, then not TEAE If stop date >= study med start date, then TEAE
	Partial	Impute stop date as latest possible date (i.e. last day of month if day unknown or 31st December if day and month are unknown), then: If stop date < study med start date, then not TEAE If stop date >= study med start date, then TEAE
	Missing	Assumed TEAE
Missing	Known	If stop date < study med start date, then not TEAE If stop date >= study med start date, then TEAE
	Partial	Impute stop date as latest possible date (i.e. last day of month if day unknown or 31st December if day and month are unknown), then: If stop date < study med start date, then not TEAE If stop date >= study med start date, then TEAE
	Missing	Assumed TEAE

 Document: MEX0114\_SAP\_v4\_4 Final Methods.docx  
 Author: [name]

 Version Number:  
 Version Date:

 Final Version 4.4  
 [17SEP2019]

 Template No: CS\_TP\_BS016 – Revision 4  
 Effective Date: 01Apr2016

Reference: CS\_WI\_BS005

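### The SAP's TEAE rule has no worsening clause, so a pre-dose adverse event that worsens or becomes serious after first dose is left out of the TEAE-based tables in both arms unless the site opened a new record

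*SAP*

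**What the plan says.** SAP 16.4.3 sets the definition: "Any AE which started at or after the first administration of study treatment will be considered a Treatment Emergent Adverse Event (TEAE". Appendix 2 turns it into an algorithm. For a known start date the rule is "If start date < study med start date, then not TEAE", repeated for known, partial and missing stop dates. The row headed "Partial, but known components show that it cannot be on or after study med start date" gives the same answer for all three stop-date types. For a missing start date SAP 16.4.3 says "If the start date is missing for an AE, the AE will be considered to be treatment emergent" and refers to Appendix 2, where the stop date decides if there is one.

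On collection, protocol 8.2 covers "All AEs (serious and non-serious) which occur from enrolment through patient participation in the study", with onset and resolution dates. Protocol 3.1 allows "a screening period including 2 or more visits during a period up to 100 days" before randomisation. On grading, protocol 8.2.2 says "For each episode, the highest severity grade attained should be reported".

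SAP 16.4.3 makes drug-relatedness conditional on emergence: "Any TEAE reported in the study having a possible, probable or highly probable relationship to study drug will be defined as" an adverse drug reaction (ADR). Protocol 8.2.1 applies the same relationship categories to any AE. Protocol 4.2.3 and 9.4.4 name AEs and SAEs as what is presented; SAP 3.2.3 and 16.4.2 name TEAEs and serious TEAEs.

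**The concern.** A TEAE definition normally has two arms: new onset after first dose, and worsening after first dose of something already present. The SAP has only the first. Because the protocol stores one grade per episode and asks for no date of grade change, a mild screening complaint that becomes severe in cycle 1 can end up as one record, graded severe, with a pre-dose onset. The algorithm rejects that record.

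At stake is the safety half of the study objective. The by-arm AE summaries in SAP 16.4.3 (by term, by severity, serious, ADR, leading to discontinuation, leading to death) are titled and built as TEAE tables. The ADR restriction carries the omission further: an event that the investigator judges possibly, probably or highly probably related is an ADR under protocol 8.2.1 but not under the SAP. Read literally, it would also leave the ADR listing. There is an internal mismatch as well: SAP 16.7 can count a patient as stopping study drug for another AE while the table of TEAEs leading to discontinuation omits the event.

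**Working it through.** The documents state no figure that depends on this rule, so there is nothing to reproduce. The check runs the algorithm, then bounds the effect.

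**1. Appendix 2 applied to an event that continues past first dose.** Seven start-date cases were crossed with three stop-date types (known after first dose, partial after first dose, missing or ongoing).

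| Start date | Result |
|---|---|
| Known, before first dose (2 dates × 3 stop types) | not TEAE, 6 of 6 |
| Partial, must precede first dose (1 × 3) | not TEAE, 3 of 3 |
| Known, on the day of first dose (1 × 3) | TEAE, 3 of 3 |
| Partial, could be on or after first dose (2 × 3) | TEAE, 6 of 6 |
| Missing (1 × 3) | TEAE, 3 of 3 |

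Events shown to have begun before dosing are rejected in 6 + 3 = 9 of 9 cases. Severity, seriousness and relationship are not inputs to any branch. An incompletely dated screening event can become a TEAE by default, but not because it worsened.

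**2. What the record contains.** Protocol 8.2 asks for onset and resolution dates, and 8.2.2 for the peak grade. Neither asks for the grade at first dose or the date of a grade change. Neither tells sites to open a new record on worsening, and neither forbids it.

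**3. Declared changes.** SAP 4.3 lists ten changes from the protocol. They cover the primary and secondary efficacy models, summary statistics, new endpoints, subgroups and C-peptide handling. None covers the move from AEs to TEAEs or the narrower ADR definition.

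**4. Size per affected patient.** Of 72 patients randomised 2:1, 72 × 2/3 = 48 receive ladarixin and 24 placebo. One patient omitted changes a by-term incidence by 1/48 = 2.1 percentage points on ladarixin, or 1/24 = 4.2 on placebo. These are maxima. SAP 16.4.3 counts a patient once per preferred term, so a patient with another post-dose episode of the same term is already counted.

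**5. Illustration, by assumption only.** The documents give no rate of AEs ongoing at first dose and no rate of worsening. Suppose 10% to 40% of patients have such an AE and 5% to 20% of those worsen:

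- Low: 48 × 0.10 × 0.05 = 0.24 ladarixin patients; 24 × 0.005 = 0.12 placebo patients.
- High: 48 × 0.40 × 0.20 = 3.84 ladarixin patients; 24 × 0.08 = 1.92 placebo patients.
- Chance of at least one ladarixin patient: 1 − (1 − 0.005)^48 = 21% at the low end; 1 − (1 − 0.08)^48 = 98% at the high end.

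**The case against.** The strongest reply is that the omission depends on site practice. Protocol 8.2.2 does not define an episode, and the CRF completion rules are not in the documents. If a site recorded the worsening as a new AE with its own onset date, the SAP rule would count it. That stands: a reader might infer that such worsening can never be treatment-emergent, and the documents do not support that.

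Three other strong readings also fail.

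- **That the event survives only in listings.** SAP 16.7 summarises reasons for stopping study drug in the Safety set, and the AE overview has a count of deaths that is not worded as limited to TEAEs. Worsening laboratory values, vital signs and QTcF appear in the change-from-baseline tables. Severe hypoglycaemia is analysed separately from randomisation.
- **That earlier ladarixin data show the scenario is likely.** In protocol 2.4.3, headache is 11 and dyspepsia 7 of 40 reported ADRs. These are shares of events, not rates of complaints present at screening. The protocol describes dyspepsia as occurring soon after dosing and recurring with further doses, which is the post-dose onset that the SAP rule does catch. All phase 1 AEs were mild or moderate.
- **That the rule favours ladarixin by design.** It applies to both arms, and no confirmatory comparison is affected.

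None of this supplies the missing clause. Where worsening stays in the original record, the written rule gives the wrong classification.

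**Conclusion.** The point holds as a defect in the rule. Under SAP 16.4.3 and Appendix 2, an AE known to have begun before first dose is not treatment-emergent even if it later worsens or becomes serious. It drops out of the TEAE, severity, serious-TEAE, ADR and TEAE-discontinuation tables in both arms, provided the worsening was kept in the same record. That proviso is a natural consequence of recording one peak grade per episode, but it is not stated. The ADR definition conflicts with protocol 8.2.1, and the narrowing from AEs to TEAEs is not declared in SAP 4.3.

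The size is unknown. The bound is 2.1 points per affected ladarixin patient for a given term. The range of 0.24 to 3.84 ladarixin patients rests wholly on assumed rates. The change is worth making because it is cheap and a single severe or serious event matters in a safety table of this size, not because the documents show that many events would be lost.

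**What to change.** 1. In SAP 16.4.3 and Appendix 2, define a TEAE as an AE that starts on or after first dose, or that starts before it and increases in severity or becomes serious on or after it.
2. Base the ADR definition on any AE, as in protocol 8.2.1, and list the remaining move from AEs to TEAEs in SAP 4.3.
3. Where sites can still do so, record worsening as a new AE with its own onset date and grade. This may be too late for most data: the SAP is dated September 2019, and protocol 3.2 projected the last visit for December 2017.
4. For data already held with peak grade only, use the blind data review planned in SAP 6. Identify pre-dose AEs ongoing at first dose that were judged at least possibly related, led to discontinuation of study drug, or show evidence of worsening or becoming serious after dosing. Do not reclassify events that were already severe or serious before dosing without such evidence. Where timing cannot be established, show them in a separate by-arm table.

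The cost is wording in two places of the SAP, a small blinded review, possibly a few extra AE records, and slightly higher TEAE counts in both arms. A SAP change alone may not recover every event, because the grade before dosing was not necessarily kept.

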#### 16.4.4. SAFETY LABORATORY EVALUATIONS

Results from the local laboratories will be included in the reporting of this study for Hematology and Blood Chemistry. Data will be summarized for the SAF set.

Presentations will use SI Units.

The following summaries will be provided for Hematology and Blood Chemistry laboratory data:

- 1) A summary table showing for all laboratory tests the values and changes from baseline to each subsequent visit by treatment group;
- 2) A summary table showing for all laboratory tests the frequency of patients reporting an out-of-range (below LLN or above ULN) laboratory value at Screening and at subsequent visits by treatment group.
- 3) A summary table showing for all laboratory tests the frequency of patients reporting an abnormal (clinically or not clinically significant) laboratory value at Screening and at subsequent visits by treatment group.

A listing showing values, the reference ranges and the clinical significance according to investigators' opinion will be produced. Laboratory data will be presented by-patient and within-patient by laboratory test and visit.

##### 16.4.4.1. Conversion of Laboratory Values Units

To convert from the conventional unit to the SI unit, multiply by the conversion factor:

Parameter	Conventional Unit	Conversion Factor	SI Unit
Hematology			
Hemoglobin	g/dL	10	g/L
Hematocrit	%	0.01	Proportion of 1.0
RBC count	$\times 10^6/\mu\text{L}$	0.1	$\times 10^{12}/\text{L}$
	$\times 10^6/\text{mm}^3$	1	
	$\times 10^3/\mu\text{L}$	1	
WBC count	$\times 10^3/\text{mm}^3$	1	$\times 10^9/\text{L}$
Neutrophils	$\times 10^3/\mu\text{L}$	1	$\times 10^9/\text{L}$

Document: MEX0114\_SAP\_v4\_4 Final Methods.docx

Author: [name]

Version Number:

Version Date:

Final Version 4.4

[17SEP2019]

Template No: CS\_TP\_BS016 – Revision 4

Effective Date: 01Apr2016

Reference: CS\_WI\_BS005

Parameter	Conventional Unit	Conversion Factor	SI Unit
	x 10  /mm 	1	
	%	x WBC/100	
	x 10  /μL	1	
Lymphocytes	x 10  /mm 	1	x 10  /L
	%	x WBC/100	
Monocytes	x 10  /μL	1	x 10  /L
	x 10  /mm 	1	
Basophils	%	x WBC/100	
	x 10  /μL	1	x 10  /L
	x 10  /mm 	1	
Eosinophils	%	x WBC/100	
	x 10  /μL	1	x 10  /L
	x 10  /mm 	1	
Platelets	%	x WBC/100	
	x 10  /μL	1	
	x 10  /mm 	1	x 10  /L
Blood chemistry			
Total Bilirubin	mg/dL	17.104	μmol/L
	g/dL	17104	
	g/L	171.04	
Aspartate aminotransferase (AST)	units/L	1	U/L
Alanine aminotransferase (ALT)	units/L	1	U/L
	g/dL	10	g/L
Serum Albumin	%	1	%
Urea	mg/dL	0.357	mmol/L
Sodium	mEq/L	1.0	mmol/L
Potassium	mEq/L	1.0	mmol/L
Serum Creatinine	mg/dL	88.4	μmol/L

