9.2. RANDOMIZATION

Patient will be randomized in a 2:1 fashion to either ladarixin or placebo.

The randomization list will be generated with a computer procedure by the method of random permuted blocks in which treatment will be balanced within centres. A master randomization list will be generated, randomizing an excess of patients (a maximum of 21 for each site) to allow competitive recruitment within each centre.

The randomization list will be prepared by an independent statistician and provided to Dompé in a sealed envelope to prevent unblinding. Similarly, the randomization list will be provided to the facility responsible for IMP packaging/labelling for the purpose of IMP preparation.

Individual treatment codes will be provided as a tamper-resistant system (either a sealed envelope or a scratch card) to:

- the Investigator for emergency procedures;
- the Pharmacovigilance for safety procedures.

Individual treatment codes must be kept in a secure location accessible only to designated staff in order to prevent dissemination of the treatment to personnel involved in study conduct who must remain blind.

The randomization code will be broken at study completion, i.e. when the last patient has completed his/her last follow-up visit, and once the database has been locked.

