* = As per Treatment discontinuation criteria, **no IMP will be dispensed** in the case: QTcF is either > 500 msec or increases by > 60 msec from screening measurement on two consecutive ECG readings taken 1 hour apart; Patient develops LBBB, or atrio-ventricular or heart block; or any significant cardiovascular disease; Patient develops renal (calculated CLcr < 60 mL/min) or hepatic (increased ALT/AST > 3 x ULN and increased total bilirubin > 3mg/dL [>51.3 µmol/L]) dysfunction as well as hypoalbuminemia; Female patient has become pregnant.

Randomization = Study Day 0 with reference to **Study Day 1 = first day when the IMP administration is started.**

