## 16.5. ECG EVALUATIONS

Data will be summarized for the SAF set.

ECG will be performed at Screening, at pre-dose visit of 2nd cycle and at pre-dose visit of 3rd cycle.

For German investigational sites only: an ECG will be performed at Day 3 to 5 of 1st treatment cycle.

If QTcF value at subsequent visit after Screening is either > 500 msec or has increased by > 60 msec from screening value, the ECG evaluation will be repeated and the repeated QTcF value will be considered as the only evaluation value for that visit.

A summary table showing for QTcF the values and changes from baseline to each subsequent evaluation will be produced by treatment group.

A summary table showing the Investigator's judgement on ECG evaluation (Normal/Abnormal NCS/Abnormal CS) will be produced at Screening and at subsequent visits by treatment group.

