## 16.7. PERMANENT TREATMENT DISCONTINUATION CRITERIA

Data will be summarized for the Safety Analysis Set (SAF).

The following measurements will be reported:

- IMP treatment completed (Yes/No)
- If No: total number of capsules administered
- If No: reason for permanent discontinuation of IMP:
  - QTcF > 500 msec or increased by 60 msec from Screening measurement on two consecutive ECG reading (1 hour apart)
  - Complete Left Bundle Branch Block (LBBB), atrio-ventricular block, complete heart block
  - Significant cardiovascular disease
  - Renal Dysfunction
  - Hepatic Dysfunction

---

Document: MEX0114\_SAP\_v4\_4 Final Methods.docx

Author: [name]

Version Number:

Final Version 4.4

Version Date:

[17SEP2019]

Template No: CS\_TP\_BS016 – Revision 4

Reference: CS\_WI\_BS005

Effective Date: 01Apr2016

Copyright © 2009, 2010, 2012, 2016 Quintiles Transnational Corp. All rights reserved.

The contents of this document are confidential and proprietary to Quintiles Transnational Corp. Unauthorized use, disclosure or reproduction is strictly prohibited.

- Hypoalbuminemia
- Pregnancy
- Other AE
- Other

The following listings of discontinuation criteria will be presented:

- Laboratory test results: Serum Creatinine, Serum Albumin, Total Bilirubin, ALT, AST (Screening, Pre-dose visit 2nd and 3rd cycle, for German Investigational sites only also Day 3-5 of 1st cycle).
- Creatinine Clearance (Screening, Pre-dose visit 2nd and 3rd cycle, for German Investigational sites only also Day 3-5 of 1st cycle).

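### SAP 16.4.4.1 converts total bilirubin from g/L with the factor 171.04, where the SAP's other rows and the protocol require 1710.4 (minor)

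*SAP*

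**What the plan says.** SAP section 16.4.4 takes its safety laboratory data from the sites: "Results from the local laboratories will be included in the reporting of this study for Hematology and Blood Chemistry". It presents them in SI units and plans, among other outputs, "A summary table showing for all laboratory tests the values and changes from baseline to each subsequent visit by treatment group". Section 16.4.4.1 supplies the conversion factors under the instruction "To convert from the conventional unit to the SI unit, multiply by the conversion factor". For total bilirubin to µmol/L these are:

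- mg/dL: 17.104
- g/dL: 17104
- g/L: 171.04

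SAP section 16.7 plans a listing relevant to the treatment-discontinuation criteria that covers "Laboratory test results: Serum Creatinine, Serum Albumin, Total Bilirubin, ALT, AST"; it does not state the units of that listing.

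The protocol gives its hepatic threshold in both units, for example in Appendix 14.3: "increased total bilirubin > 3mg/dL [>51.3" µmol/L. The same pair appears in the exclusion criteria (5.2) and in the criteria for stopping the study drug (6.3.2).

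**The concern.** Three factors for one analyte, all leading to the same SI unit, must stand in the ratios of the units they start from. The g/L factor does not. It is an operative rule, because the laboratories are local, their units may differ, and this table is what brings them to a common scale.

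At stake is the accuracy of the bilirubin values and changes in the safety tables for any patient whose laboratory uses g/L. Bilirubin is half of the protocol's hepatic criterion, so a reader will look for it. The independent double programming in SAP section 5 would not necessarily expose the error: if both programmers apply the same written constant, their datasets agree.

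**Working it through.** **Inputs**

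- SAP 16.4.4.1: 17.104 (mg/dL), 17104 (g/dL), 171.04 (g/L), each to µmol/L.
- Protocol 5.2, 6.3.2 and Appendix 14.3: 3 mg/dL corresponds to 51.3 µmol/L.
- Unit identities: 1 g/dL = 1000 mg/dL; 1 g/L = 100 mg/dL = 0.1 g/dL.

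**Step 1. Reproduce the rows that are sound.**

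- From mg/dL to g/dL: 17.104 × 1000 = 17104, as the SAP states.
- Against the protocol: 3 × 17.104 = 51.312, which rounds to the protocol's 51.3.

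**Step 2. Derive the g/L factor by three routes.**

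- From the mg/dL row: 17.104 × 100 = 1710.4.
- From the g/dL row: 17104 × 0.1 = 1710.4.
- From the protocol alone: (51.3 / 3) × 100 = 1710, equal to 1710.4 within the rounding of 51.3.

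**Step 3. Compare with the stated factor.** 1710.4 / 171.04 = 10. Equivalently, the g/dL and g/L factors should differ by 10, but 17104 / 171.04 = 100. The stated factor is low by exactly ten.

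**Step 4. Effect on one patient, if the laboratory reports in g/L.** The protocol's threshold of 3 mg/dL is 0.03 g/L.

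| Factor | Calculation | Shown as (µmol/L) |
|---|---|---|
| 171.04 (SAP) | 0.03 × 171.04 | 5.1 |
| 1710.4 | 0.03 × 1710.4 | 51.3 |

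Read the other way, a g/L result would be shown as 51.3 µmol/L only at 51.3 / 171.04 = 0.30 g/L, which is 30 mg/dL. A change from baseline is a difference of two values multiplied by the same factor, so it too is shown at one tenth of its size.

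**Step 5. A neighbouring cell to confirm.** The same table appears to give red cells in ×10⁶/µL the factor 0.1 and in ×10⁶/mm³ the factor 1. Since 1 µL = 1 mm³, these are the same unit, and 10⁶ per 10⁻⁶ L is 10¹² per L, so both factors should be 1. In the text version of the SAP the rows here are visibly displaced (a ×10³/µL row falls among the red-cell rows), so this is a cell to look up, not an established error.

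**The case against.** The strongest reply is that the error may touch nobody. Neither document says that any laboratory reports bilirubin in g/L; results in mg/dL or g/dL convert consistently. Even if a laboratory does use g/L, several outputs are protected. Out-of-range flags are right as long as the value and its reference range are in the same unit, and the clinical-significance table rests on the investigator's judgement. All of this stands, and it is why the point is minor.

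It can also be said that the cell may have been misread from the PDF. That is worth a look but unlikely: the unit and factor share a row, and 171.04 contains every digit of 1710.4 with only the decimal point moved, so a single lost character would not produce it.

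Three stronger conclusions are tempting, and the documents support none of them.

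- *That the hepatic stopping rule would be misapplied.* Protocol 7.2.2 has sites act on their own laboratory results before dispensing, against a threshold given in both mg/dL and µmol/L. The SAP table is used for reporting and does not enter those decisions.
- *That the pooled bilirubin means or the treatment comparison would shift by a known amount.* No affected laboratory or number of patients is given. Nor can one assume that the arms would move together: Protocol 9.2 describes a list made "by the method of random permuted blocks in which treatment will be balanced within centres", while SAP 8.2 says randomization is not stratified by centre.
- *That the red-cell factor is a second proven error.* The displaced rows do not allow that conclusion.

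**Conclusion.** The g/L factor for total bilirubin is wrong as written: the SAP's two other rows and the protocol's threshold pair all lead to 1710.4. Any bilirubin reported in g/L would be tenfold too low in the SI-unit summaries of values and changes from baseline, and in the SAP 16.7 listing if that listing is converted.

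The arithmetic needs nothing beyond the documents' own figures. The practical effect depends on one fact they do not give: whether any local laboratory reports in g/L. If none does, the effect is nil. The primary analysis does not use this table. Severity: minor.

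**What to change.** 1. Confirm the bilirubin g/L cell in the issued SAP and set the factor to 1710.4.
2. In the same check, confirm that red cells in ×10⁶/µL carry the factor 1, as for ×10⁶/mm³, and correct the cell if it does not.
3. Before database lock, list the reported unit by laboratory and test, and check the converted values for plausibility, for example against the laboratory reference ranges that SAP section 5 says come with the data transfer.
4. State in SAP 16.7 whether its laboratory listing is in reported or SI units.

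The cost is one corrected constant, one cell to confirm, one clarifying statement and one check before lock. No new data are needed, and nothing changes in patient management or the primary analysis.
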